### **Sampling and sample size**

Our target will be all patients with hyperkalemia presenting to the emergency departments in both hospitals. The Sample size was calculated based on a study published in Critical Care Explorations Journal 2020 with the article named *Comparison of IV Insulin Dosing Strategies for Hyperkalemia in the Emergency Department* by **Kayvan Moussavi** et al (8). The anticipated effect size  $d = 0.2$  with alpha error prob = 0.0250 (one-side), actual power 90, Standard deviation of 0.62 and allocation ratio 1:1. The calculated sample size is 320 (160 in each arm). Our statistician estimated a 5% drop rate. So the sample size increased to 336 (168 in each arm).

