### **3. Objectives and hypothesis of the study:**

#### **Primary outcome:**

1. To study the efficacy of two intravenous insulin doses (5 units and 10 units) in reducing serum potassium level in patients receiving hyperkalemia treatment using the main laboratory measurements. (the aim of reduction of 0.6 mmol/l +/- 0.2 mmol/L) (1). Blood sample will be collected and send to the main laboratory for analysis at two hours from medications administration. The efficacy of the 2 doses will be measured at 2 hours from administration of medications by comparing the amount of changes in potassium level at two hours.

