## Study hypothesis

No difference between 5 and 10 units of intravenous regular insulin in lowering potassium levels in patients with hyperkalemia at 2 hours.

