## Rationale for the choice of sample size

The Sample size was calculated based on a study published in Critical Care Explorations Journal 2020 with the article named Comparison of IV Insulin Dosing Strategies for Hyperkalemia in the Emergency Department by Kayvan Moussavi et al (8). The anticipated effect size  $d = 0.2$  with alpha error prob = 0.0250 (one-side), actual power 90, Standard deviation of 0.62 and allocation ratio 1:1. The calculated sample size is 320 (160 in each arm). Our statistician estimated a 5% drop rate. So the sample size increased to 336 (168 in each arm).

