5 versus 10 units of insulin in hyperkalemia management: multi-center, prospective, double blinded, non-inferiority, randomized control trial in adult patients with age of 18 years and more at two emergency departments Sultan Qaboos university hospital and Royal hospital. We will include patients with potassium level 5.5 mEq/l and more. We will measure the mean reduction of insulin level among both groups at 2 hours from treatment. Written consent will be obtained from all patients. Eligible subjects will be enrolled. Control group will receive 10 units intravenous insulin with Dextrose 50 % 50 ml over 15 minutes and Salbutamol nebulization. Intervention group will receive 5 units intravenous insulin with Dextrose 50 % 50 ml over 15 minutes and Salbutamol nebulization. Patient will be monitored and basic labs will be recorded. Blood sugar will be monitored at 0, 60 and 120 (2 hours) minutes. Potassium level will be measured at presentation and at 120 minutes (2 hours) from insulin administration.

Sample size calculation

We aim to study all hyperkalemia patients who come to the emergency departments of both hospitals. The sample size determination was influenced by a 2020 article in the Critical Care Explorations Journal titled "Comparison of IV Insulin Dosing Strategies for Hyperkalemia in the Emergency Department" authored by Kayvan Moussavi and colleagues. We expect an effect size of $d=0.2$, with an alpha error probability of 0.0250 (one-sided), a true power of 90, a standard deviation of 0.62, and a 1:1 allocation ratio. The sample size deduced is 320, split evenly between both groups. Anticipating a 5% attrition rate, we've adjusted our total sample to 336 participants, with 168 in each group

Aims and objectives

The aim of this study is to compare the efficacy of two insulin doses (5 units and 10 units) in reducing serum potassium level in patients receiving hyperkalemia treatment.

Outcomes

Primary outcome

- To study the efficacy of two intravenous insulin doses (5 units and 10 units) in reducing serum potassium level in patients receiving hyperkalemia treatment using the main laboratory measurements. (the aim of reduction of 0.6 mmol/l +/- 0.2 mmol/L) (1). Blood sample will be collected and send to the main laboratory for analysis at two hours from medications administration. The efficacy of the 2 doses will be measured at 2 hours from administration of medications by comparing the amount of changes in potassium level at two hours.

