Secondary outcomes

1. Study the mean difference of the response to the anti-hyperkalemic measures based on the level of initial potassium (serum potassium before given any medications – At baseline) (the investigators will categorize potassium level into groups mild (5.5–6 mmol/l), moderate (6–6.5 mmol/l) and severe (>6.5 mmol/l) and will see the mean difference in reduction in potassium level in between the 2 doses).
2. Association of mean potassium reduction with initial blood sugar level (blood sugar level before given any medications – At Baseline) on potassium reduction (the investigators will categorize blood sugar into groups: Below 10mmol/L, 10.1-14.9 mmol/L, and 15 – 19.9mmol/L among each group the investigators will see the mean potassium reduction level).
3. Incidence of hypoglycemia (random blood sugar (RBS) \leq 3.89 mmol/l in Diabetic patients and less than 3 mmol/l in non-Diabetic patients) (12). (and risk factor Characteristic of patients of higher risk of developing hypoglycemia (the investigators will investigate which group of patients will have a high risk of hypoglycemia ((e.g: initial Glucose level, initial creatinin/renal function, comorbidities, type of dialysis...)).

Safety outcomes

Adverse events are reported at each visit.

Populations

Intention-to-treat (ITT)

All randomized study subjects. This will be seen as the primary population for the analysis.

Per Protocol (PP)

All randomized study subjects completing the whole study period (complete cases). For a specific analysis, study subjects with missing data on any of the variables in the model will be excluded from the analysis. Analyses of this population is seen as a sensitivity analysis to investigate whether conclusions are sensitive to assumptions regarding the pattern of missing data.

Statistical analysis

Primary outcome

The data analysis for the clinical trial will be conducted using IBM SPSS Statistics version 29.0. Categorized variables will be presented as percentages, and continuous variables will be presented as means with standard deviations or medians with interquartile ranges. The primary outcome, the reduction in serum potassium levels, will be analyzed using a linear mixed effect model that adjusts for baseline potassium levels. A p-value of <0.05 will be considered statistically significant.

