The intention-to-treat (ITT) analysis will include all subjects who provide at least one post-baseline valid measurement. The per-protocol (PP) analysis will only include subjects who have completed the study according to the protocol and who have valid measurements for all time points. Non-inferiority will be concluded if both the ITT and PP analyses show that the difference in means between the two treatment groups is not statistically significant and lies above the margin of -20 units.

Secondary outcomes

Normally distributed continuous variables will be compared between the groups using Independent 't' test or else with Mann-Whitney 'U' test and categorized levels will be compared using chi-square test. The incidence of hypoglycemia will be presented using percentage with 95% confidence interval. A p-value of <0.05 will be considered as statistical significance.

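### The stated 90% power does not follow from the stated inputs: 160 per arm gives about 82% if 0.2 is a margin in mmol/L, and about 43% if d = 0.2 is standardised

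*Protocol*

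**What the plan says.** The sample size justification appears three times with the same numbers.

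- Protocol section 5, Sampling and sample size, sets d at 0.2. The other inputs and the result read: "with alpha error prob = 0.0250 (one-side), actual power 90, Standard deviation of 0.62 and allocation ratio 1:1. The calculated sample size is 320".
- Protocol section 20, Rationale for the choice of sample size: the same inputs, then "The calculated sample size is 320 (160 in each arm). Our statistician estimated a 5% drop rate", which raises the total to 336 (168 per arm).
- SAP, Sample size calculation: "We expect an effect size of $d=0.2$, with an alpha error probability of 0.0250 (one-sided", followed by "a true power of 90, a standard deviation of 0.62, and a 1:1 allocation ratio. The sample size deduced is 320".

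Four other statements bear on how 0.2 should be read.

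- Protocol section 3, Primary outcome, prints 0.2 with a unit, but as a tolerance: "the aim of reduction of 0.6 mmol/l +/- 0.2 mmol/L".
- Protocol section 3, Study hypothesis: "No difference between 5 and 10 units of intravenous regular insulin in lowering potassium levels".
- SAP, Statistical analysis, Primary outcome: the potassium reduction "will be analyzed using a linear mixed effect model that adjusts for baseline potassium levels".
- The same SAP section concludes non-inferiority if, in both the ITT and the PP analysis, the difference "is not statistically significant and lies above the margin of -20 units".

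Neither document calls 0.2 a non-inferiority margin, gives a formula, or mentions an allowance for covariate adjustment in the sample size text.

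**The concern.** Alpha, power, SD, allocation ratio and effect size together fix the sample size of a two-group comparison of means. All five are stated, so the 160 per arm can be checked, and it does not come out on either reading of 0.2.

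In a non-inferiority trial, a 90% claim means a 10% risk of failing to show non-inferiority when the doses are truly equal. If the real risk is 18% or 57%, an inconclusive result would be judged against a power figure that the inputs do not support. Because 0.2 has no stated unit or role, a reader also cannot tell which margin the trial was sized to exclude.

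**Working it through.** **Inputs.** From the sample size text: 0.2, SD 0.62 (no unit given; mmol/L assumed), one-sided alpha 0.025, power 90%, 1:1 allocation, 160 evaluable per arm. From the study hypothesis: true difference 0. The base case has no covariate adjustment, since the sample size text mentions none.

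**Attempt to reproduce 160 per arm.** For one-sided alpha 0.025 and 90% power, (1.95996 + 1.28155)² = 10.507.

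- 0.2 as a margin in mmol/L: n per arm = 2 × 10.507 × 0.62² / 0.2² = 202.0 (noncentral t: 203).
- 0.2 as a standardised difference: n per arm = 2 × 10.507 / 0.2² = 525.4 (noncentral t: 527).

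Neither is 160.

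**Power at the stated size.** For the mmol/L reading, SE = 0.62 × √(2/160) = 0.0693, so 0.2/0.0693 = 2.885. Power is Φ(2.885 − 1.960) = Φ(0.925) = 82.3%. For the standardised reading, 0.2 × √(160/2) = 1.789, and power is Φ(1.789 − 1.960) = Φ(−0.171) = 43.2%. The noncentral t gives slightly lower values:

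| Reading of 0.2 | Power, 160 per arm | Power, 168 per arm | n per arm for 90% |
|---|---|---|---|
| Margin in mmol/L, SD 0.62 | 82.0% | 83.8% | 203 |
| Standardised d | 43.0% | 44.7% | 527 |

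**Could something else explain 90%?**

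- *One-sided alpha 0.05, 0.2 mmol/L.* Power at 160 is 89.1%. For 90%, n = 2 × (1.64485 + 1.28155)² × 0.62² / 0.2² = 164.6 (noncentral t: 166). This is the nearest match and may be where the figure came from, but that is inference, and all three places state 0.025.
- *Baseline adjustment.* By the normal approximation, 90% at 160 per arm needs a residual SD of 0.2 / (3.2415 × √(2/160)) = 0.552 (noncentral t: 0.550). If 0.62 is the unadjusted SD, the required correlation of baseline with outcome is √(1 − (0.550/0.62)²) = 0.46. No correlation is stated. Assumed values, with adjusted SD = 0.62 × √(1 − r²):

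| Assumed r | Adjusted SD | Power at 160 |
|---|---|---|
| 0.2 | 0.607 | 83.5% |
| 0.3 | 0.591 | 85.4% |
| 0.4 | 0.568 | 88.1% |

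- *A different margin.* At SD 0.62, 160 per arm has 90% power for 0.62 × 3.2415 × √(2/160) = about 0.225 mmol/L. This figure appears in neither document.
- *The SAP margin.* Read in mmol/L, 20/0.62 = 32.3 SDs. It cannot have produced 160 per arm.
- *320 read as per arm.* Power would be 98.3% (mmol/L) or 71.6% (standardised); neither is 90%.

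**Effect of the SAP decision rule.** The rule also requires a non-significant difference. With a 0.2 mmol/L margin and two-sided 5% significance, the estimate must lie between −0.2 + 1.96 × 0.0693 = −0.0641 and 1.96 × 0.0693 = 0.1359. At a true difference of 0 that has probability 79.8% in one population, before the requirement that ITT and PP both succeed.

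**The case against.** The strongest reply is that the mmol/L reading is the natural one. A standardised d needs no SD, yet 0.2 is paired with 0.62, and the Primary outcome section prints 0.2 in mmol/L. On that reading the shortfall is 82% against 90%, or 83.8% if all 168 per arm are evaluable. Many would accept that as adequate power. Type I error and the randomised comparison are untouched, and the confidence interval will show what was excluded whatever the plan claimed. Baseline adjustment is prespecified and will recover some power: at 168 per arm with an assumed correlation of 0.4, power is 89.6%.

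Much of this stands. The mmol/L reading is the better supported, and 43% should be taken as the result of the literal wording, not as the likely truth. But the documents do say effect size d, and nothing in them settles the question. Baseline adjustment may close the gap, yet the correlation it needs is not written down, and whether 0.62 is already an adjusted SD depends on a cited study that is not part of the documents. Nor is a true difference of zero a pessimistic choice. It is the Protocol's own hypothesis, and the Introduction describes the study used for the sample size as finding less potassium reduction below 10 units. None of these points makes the stated figures agree.

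It is also fair to say that the SAP margin and its non-significance condition are separate defects. They matter here only because the 0.2 has to be reconciled with them.

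**Conclusion.** The point holds. The stated inputs do not give 90% power at 160 per arm on either reading: about 82% if 0.2 is a margin in mmol/L (8 points short) and about 43% if it is standardised (47 points short). The corresponding risks of missing true non-inferiority are about 18% and 57%, against the 10% implied.

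These figures assume a true difference of zero, an SD of 0.62 in mmol/L for the first reading, one-sided alpha 0.025, no covariate adjustment, and non-inferiority judged from the confidence limit alone. At least one stated figure, or an unstated assumption, must change. The documents do not show which. Because this is the trial's central design claim and it is repeated in both documents, it has to be corrected.

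**What to change.** 1. The trial statistician retrieves the original calculation and states the unit and role of 0.2.
2. The same person reconciles 0.2 with the margin and decision rule in the SAP's Primary outcome analysis. This comes before any new power statement, because keeping the non-significance condition would lower the mmol/L figure to about 79.8% in one population.
3. Whichever figure is wrong (power, alpha, SD or 0.2) is corrected identically in Protocol section 5, Protocol section 20 and the SAP's Sample size calculation.

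If 0.2 mmol/L is confirmed as the margin, and non-inferiority is judged from the confidence limit alone, suitable wording is:

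> About 82% power for a non-inferiority margin of 0.2 mmol/L, SD 0.62 mmol/L, one-sided alpha 0.025, true difference 0, 160 evaluable patients per arm, without covariate adjustment.

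With that margin, SD and alpha, 90% can stay only if the residual SD (at most about 0.55) and the baseline correlation (about 0.46, if 0.62 is unadjusted) are written down with their source. If the original calculation shows another alpha or margin, that value should be stated and justified in place of the present one. If d proves to be standardised, the restated power is about 43%, and the plan should say so openly.

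The cost is one check by the statistician and a change of wording in three places, plus the SAP reconciliation. The correction itself requires no extra patients and no change to treatment. The price is a less favourable power figure, unless the original calculation supports 90%.

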## **6. Randomization**

When a patient has hyperkalemia ( $K \geq 5.5$  mEq/L) our doctor/investigator will come to explain the research to the patient/relatives and after explaining all details a written consent will be signed. Our doctor/investigator will take a random envelope from the study box to randomize the patient between 5 units or 10 units of insulin with 50 ml of 50% Dextrose and salbutamol Nebulization. The doctor will take the envelope code and place it on the data collection sheet without looking into the instructions. The Doctor will give the nurse that envelope. Each envelope will have instructions about the medications administration route and dose (see appendix: [medications administration form](#)). The Nurse will administer the medications with the documentation of starting time. Then our doctor will follow the patients and lab results for 2 hours based on the ACEP and Ministry of Health/Royal hospital protocol.

Randomization codes will be done by an online free site for having unique codes (<https://www.randomcodegenerator.com/en/generate-codes>). Eligible participants after obtaining consent will be randomly assigned to either 5 units of Intravenous insulin or 10 units of intravenous insulin. The researcher and patient will not know the dose of insulin administered.

## **7. Study flow**

The study protocol will be for a total of 2 hours. All groups will follow the same path except the dose of insulin administered. After the result of potassium level ( $\geq 5.5$  mEq/L) patient will be screened for inclusion and exclusion criteria at the same time all other medications except insulin can be administered as the doses are fixed. Eligible patient will have to sign a

written consent if they agreed to be involved in our study. The initial data and basic labs will be collected before starting the study protocol. The incharge doctor/investigator will take the random code and write it on the data collection sheet of that patient from already prepared list/code and give the assigned nurse the medications administration card/form (see appendix: [medications administration form](#)).

Every patient will receive:

- Potassium lowering agent:
    - Intravenous Regular insulin 5 units **OR** 10 units with Glucose 50% water 50 ml over 30 minutes according to the randomization.
    - Salbutamol nebulization 10 mg in 3ml normal saline over 15 minutes.
  - The physician will decide the need of cardiac stabilizing agents (e.g Calcium Gluconate) as indicated by the physician in-charge of the patient.
- Please see [study flow chart](#) in the attachment.

5 Units insulin group	10 units insulin group
Medications to be administered: • IV Insulin Regular 5 units with Dextrose 50 % 50 ml over 30 minutes. • Salbutamol 10 mg NEB over 15 minutes.	Medications to be administered: • IV Insulin Regular 10 units with Dextrose 50 % 50 ml over 30 minutes. • Salbutamol 10 mg NEB over 15 minutes.

Figure 1: Treatment. RBS: Random Blood sugar. IV: Intravenous. NEB: Nebulization.

Initial investigations will include:

ECG, Urea and electrolytes, Creatinine, eGFR, Random blood sugar, complete blood count, Magnesium level, bone profile, phosphate level, will be attached if not sent before.

Repeated labs will be with these frequencies:

**Potassium** level: 0 and 120 minutes from medications administration time.

**Blood sugar**: 0, 60 and 120 minutes from medications administration time.

The study will be over at 2 hours (120 minutes) or by patient decision to withdraw from the study.

	0	Post involvement	
		60	120
Timeline (minutes) from medications administration	0	60	120
Eligibility screen	*		
Consent	*		
Randomization	*		
Basic labs: ECG, U&E, RBS, CBC, Mg, bone profile, PO4, VBG.	*		
Study Medication administration	* →		
Other medications as indicated	* →		
Serum Potassium measurement	*		*
Serum Glucose measurement	*	*	*

Figure 1: Schedule for evaluation time-line. ECG: electrocardiography, U&E: Urea and electrolytes, RBS: Random blood sugar, CBC: complete blood count, Mg: Magnesium, PO4: phosphate, VBG: Venous Blood Gas.

## 8. Study treatment.

### Medications for study treatment.

#### Regular insulin/ Dextrose 50%

Subjects in the emergency department with hyperkalemia will be administered regular insulin either 5 units or 10 units.

After identifying appropriate adult patients, obtaining written consent (Appendix: [Written Informed consent](#)), and labs confirmed that patient is having hyperkalemia. antihyperkalemic measures will be started, Regular insulin (5units or 10units) will be administered according to the steps below.

#### Method for Application of Intravenous Regular Insulin 5 units

1. Perform hand hygiene and don clean gloves.
2. Draw the 5 units of regular insulin.
3. Mix it with 50ml of dextrose 50%.
4. Connect to placed venous cannula.
5. Run it no less than 5 seconds (proposed 30 minutes)
6. Disconnect and discard all materials in their proper disposal bins.
7. Remove gloves and perform hand hygiene.

#### Method for Application of Intravenous Regular Insulin 10 units

1. Perform hand hygiene and don clean gloves.
2. Draw the 10 units of regular insulin.
3. Mix it with 50ml of dextrose 50%.
4. Connect to placed venous cannula.
5. Run it no less than 5 seconds (proposed 30 minutes)
6. Disconnect and discard all materials in their proper disposal bins.

7. Remove gloves and preform hand hygiene.

## Salbutamol

### Method for Application of Salbutamol Nebulization

1. Preform hand hygiene and don clean gloves.
2. Take 10 mg of insulin.
3. Mix it with 3 ml of Sodium Chloride 0.9%.
4. Put it on Nebulization devise.
5. Run it for 15 minutes
6. Disconnect and discard all materials in their proper disposal bins.
7. Remove gloves and preform hand hygiene.

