### Each package contains:

- **Envelope with:**
  - o Data collection sheet with unique generated number.
  - o Consent form.
  - o Instructions sheet
  - o Medication administration form (for the nurses).

Blood investigation will be sent to biochemistry lab for potassium level and other investigations, and it's the only acceptable way in the study. The study investigators will verify that study treatments are received intact and in the correct amounts.

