## 22. Quality control and quality assurance.

### Preparation quality

- A study approval from the Royal Hospital and Sultan Qaboos University hospital review board obtained.
- Ensure that all required documents (data collection sheet, informed consent), randomization packages are in order and easily accessible for the investigators.
  - o **Investigator's brochure**
- To document that relevant and current scientific information about the investigational product has been provided to the investigator.
  - o **Signed protocol.**
  - o **Informed consent form.**
  - o **Subject Deviation/Unanticipated Problem Case Log.**
  - o **Serious Adverse Event (SAE) Case Log.**
  - o **Withdrawal log.**

- **Nurses and physicians who are involved in the data collection will be trained in the following areas:**
  - o Full description of the attended study and the way to obtain research consent.
  - o Obtaining potassium level from official biochemistry lab result
  - o Preparing Intravenous insulin/Dexstrose 50% + Salbutamol Nebulization.
  - o Measurement of possible side effected and secondary outcomes.

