**During research progress regular visits from the principle investigator will be done ensuring the following:**

- Informed Consent forms are properly completed and up to date.
- Participants are appropriately screened and enrolled.
- Inclusion and exclusion criteria are applied properly.
- Randomization procedures are followed, and the blind is maintained.
- Trial assessments and treatment are conducted in compliance with the protocol.
- All source documents are attributable, legible, contemporaneous, original, accurate, and complete.
- Medication dosing and documentation are following the protocol.
- All adverse events and serious adverse events have been documented and appropriately reported to the principle Investigator and Institutional review board.
- Reviewing drug accountability records for completeness and accuracy.
- Checking for protocol deviations/violations that may have occurred.
- Following up on unresolved issues from previous visits.
- Providing, or arranging for, additional staff training in problem areas.

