### Medications administration card

(Insulin 5 units group)

- The doctor **must not know** the dose of insulin received by the patient.
- Give the patient the following medications:
  - Insulin Regular 5 units with Dextrose 50 ml of 50 % concentration intravenously (IV) over 30 minutes.
  - Salbutamol 10 mg Nebulization over 15 minutes.

Please repeat potassium level after 120 minutes from the time insulin/dextrose infusion

Repeat RBS: 60 and 120 minutes.

	60 minutes	120 minutes
Serum Potassium measurement		*
*RBS via glucometer	*	*

- If a patient become hypoglycemic (random blood sugar (RBS)  $\leq$  3.89 mmol/l in Diabetic patients and less than 3 mmol/l in non-Diabetic patients) inform the Doctor/Research assistant.
- Example: if you start insulin/Dextrose at 02:00 the infusion till 02:30 so repeat RBS at 03:00 and 04:00. Repeat U&E at 04:00.
- \*RBS: Random blood sugar. U&E: urea and electrolytes.

Study Flow chart:

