## Attending physician

1. Patient will receive Salbutamol nebulization 10 mg in 3ml normal saline over 15 minutes.
2. ((The physician will decide the need of cardiac stabilizing agents (e.g Calcium Gluconate) as indicated by the physician in-charge of the patient.))
3. Will screen inclusion and exclusion criteria.
4. Explain all study procedure to the patient.
5. Obtain informed consent with signature.

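### Step 2 of the salbutamol nebulisation procedure names insulin instead of salbutamol

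*Protocol*

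**What the plan says.** Protocol section 8 has three numbered procedures: intravenous insulin 5 units, intravenous insulin 10 units, and salbutamol nebulisation. Step 2 of the third reads "Take 10 mg of insulin". The next steps mix it with 3 ml of 0.9% sodium chloride, place it in the nebuliser and run it for 15 minutes.

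Elsewhere the nebulised drug is salbutamol:

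- Section 7, Study flow, lists for every patient "Salbutamol nebulization 10 mg in 3ml normal saline over 15 minutes".
- The study flow chart in the appendix, under the attending physician's tasks, says "Patient will receive Salbutamol nebulization 10 mg in 3ml normal saline over 15 minutes".
- The medications administration card in the appendix says "Salbutamol 10 mg Nebulization over 15 minutes".

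Staff work from several texts. Under section 6, "Each envelope will have instructions about the medications administration route and dose", and the doctor hands that envelope to the nurse. Section 9 also lists an "Instructions sheet" in each package, and section 22 lists training in "Preparing Intravenous insulin/Dexstrose 50% + Salbutamol Nebulization". The protocol reproduces neither the instructions sheet nor the training content.

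**The concern.** A preparation step that names the wrong drug is a medication-safety hazard even when the intent can be worked out. The drug named in error is the trial's own study drug, which is at hand for every patient. The procedure directly above, for 10 units of intravenous insulin, also has drawing up insulin as its step 2 and also uses the number 10. If someone followed the salbutamol step as printed, the patient would be given insulin by nebuliser and would miss a potassium-lowering co-treatment meant for everyone.

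There is a smaller point about monitoring. Section 22 has the principal investigator's visits confirm that "Medication dosing and documentation are following the protocol". Section 24 counts incorrect drug administration as a protocol violation and requires every violation to be documented. A step that contradicts the rest of the protocol is a poor reference for those checks.

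**Working it through.** No arithmetic beyond a count applies, because nothing here depends on alpha, power, margin or sample size. The check sets step 2 beside every other place that gives the salbutamol dose.

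| Place in the protocol | Drug and amount | Saline | Duration | Times stated |
|---|---|---|---|---|
| Section 8, salbutamol procedure | **insulin** 10 mg | 3 ml | 15 min | 1 |
| Section 5, Control Group | salbutamol 10 mg | 3 ml | 15 min | 1 |
| Section 5, Intervention Group | salbutamol 10 mg | 3 ml | 15 min | 1 |
| Section 7, Study flow (list, and both columns of the treatment table) | salbutamol 10 mg | 3 ml (list only) | 15 min | 3 |
| Appendix, medication card, first copy | salbutamol 10 mg | not given | 15 min | 1 |
| Appendix, medication card, second copy | salbutamol 10 mg | not given | 15 min | 1 |
| Appendix, flow chart, attending physician | salbutamol 10 mg | 3 ml | 15 min | 1 |

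1. **Count.** Salbutamol 10 mg is stated 1 + 1 + 3 + 1 + 1 + 1 = 8 times in six places. Insulin 10 mg is stated once.
2. **Agreement on the other details.** All six places match the section 8 procedure on 10 mg and 15 minutes. Four of the six also match on 3 ml of saline. Only the noun differs.
3. **Unit and route.** The two insulin procedures in section 8 dose insulin in units, 5 or 10, intravenously with 50 ml of 50% dextrose. An insulin amount in mg, or insulin by nebuliser, matches no insulin order in the protocol.
4. **Any correcting text.** No other numbered procedure for preparing the nebuliser appears in either document. Section 22 mentions training but gives no steps. The SAP (Study design) names salbutamol nebulisation without dose or steps.
5. **Effect of the correction.** With salbutamol in place of insulin, step 2 agrees with all six places.
6. **Effect on the comparison.** The Control Group and Intervention Group paragraphs give the same nebulised treatment, so the slip creates no planned difference between arms.

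**The case against.** The strongest reply is that this is a typing error that nobody would act on. The heading of the procedure names salbutamol. Insulin is dosed in units elsewhere, so an order in mg should stop any nurse. The reproduced card names salbutamol. Section 7 allows the other medications, but not insulin, to be given while the patient is being screened, and the flow chart puts salbutamol ahead of screening, consent and randomisation. A literal reading would therefore conflict with the protocol on timing as well as on drug. A monitor reading the whole protocol would hardly record correct use of salbutamol as a violation. The unreproduced instructions sheet may also contain correct steps.

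Most of this stands. The intent is not in doubt, literal execution is unlikely, and the monitoring point is secondary. The statement that this is the only numbered preparation text holds for the two documents reviewed, not for materials that they do not reproduce.

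It does not follow that the step can be left as it is. The safeguards lie outside the step, and none of them changes what it says. The card is only partly verifiable: both reproduced copies are headed for the 5-unit group, and the 10-unit card is not shown. That is no evidence that the 10-unit card is wrong, but it does mean the card should be checked.

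**Conclusion.** The concern holds. Step 2 names the wrong drug, and the protocol's own text shows this, with eight statements of salbutamol 10 mg against one of insulin 10 mg. The error is one noun in one of seven steps.

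The procedure covers all 336 planned patients (168 per arm). That is the reach of the text, not a number of expected errors, and the documents give no basis for estimating how likely an error is.

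It should be fixed because it is a wrong-drug instruction in an operative step. It is not evidence that nebulised insulin was ever intended. It does not touch the treatment contrast, the sample size, the endpoint or the analysis. The conclusion rests only on comparing the printed texts and needs no outside assumption.

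**What to change.** Change step 2 of the salbutamol procedure in Protocol section 8 to read: *Take 10 mg of salbutamol.*

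Then check three items that the protocol does not reproduce, in case the wording was carried over: the instructions sheet in each package (section 9), the preparation training (section 22) and the medication card for the 10-unit group (appendix).

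The cost is a one-word protocol correction and a short document check. Nothing in the design, sample size or analysis changes.
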